**C. Indicators related with the clinical training of health care staff for improvement of hypertension care**

Indicator	Numerator	Denominator	Data Source	Breakdown	Frequency of collection
32. Realized trainings	Number of realized training sessions for health care staff	Number of programmed training sessions for health care staff	Training plan List of attendance	Type of training	Annual
33. Trained health care professionals	Number of trained professionals	Total number of professionals	Training plan List of attendance	Type of health professional Type of training Health facility	Annual

34. Effectiveness of training in improving clinical knowledge	Average post-test score minus average pre-test score	NA	Pre- and post-test	Type of health professional Training session Health facility	Once
35. Effectiveness of training on acquiring BP measurement skills	Number of trained professional passing post-training practical test	Total number of trained professionals undergoing post-training practical test	Post-training practical test for certification on BP measurement following international standards	Type of health professional Health facility	

**D. Indicators related with the management of the pharmacy service to guarantee the availability of the essential anti-hypertensive medication**

Indicator	Numerator	Denominator	Data Source	Breakdown	Frequency of collection
36. Notification on availability of core set of anti-hypertensive drugs	Total number of notifications made in a month	Number of weeks in the respective month	Register of notification at the pharmacy service	Type of health facility	Monthly
37. Number of weeks without availability of essential antihypertensive drugs	Number of weeks without availability of one or more essential antihypertensive drugs	NA	Pharmacy inventory	Type of health facility Name of the antihypertensive	

**E. Indicators related with patients and community engagement for improving hypertension care and the prevention of cardiovascular diseases**

Indicator	Numerator	Denominator	Data Source	Breakdown	Frequency of collection
38. Attendance to peer support group	Number of hypertensive patients who participate in the meetings of the peer support group	Number of hypertensive patients enrolled in the CVRP eligible for peer support and referred	Attendance list Denominator: Billing and electronic clinical records of Metrosalud	Sex, age, pharmacological treatment (yes, no), hypertension control (yes, no), health facility, cardiovascular risk level	Quarterly
39. Prevalence of high BP among population screened by the Community Hypertension Outreach Group (CHOG)	Number of people with high BP readings during the screening	Number of screened people for hypertension by the CHOG	Report of activities by the social worker of Metrosalud	Kind of environment, place, target population	Monthly
40. Meetings of the CHOG	Number of meetings of the CHOG	NA	Report of activities by the social worker of Metrosalud List of attendance	NA	Quarterly
41. Participation of community leaders in the meetings of the CHOG	Number of community leaders participating in the meetings of the CHOG	Total number of community leaders in the CHOG	Report of activities by the social worker of Metrosalud List of attendance	NA	Quarterly

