#### A.3. Improvement of clinical management of patients with hypertension

A.3.1. Creation of the cardiovascular risk team (CVRT), which will include the head and one leading medical doctor of the hospital unit, and the coordinating doctors of the two health centres. The CVRT will be responsible of supervising good clinical management of hypertension. It will conduct audits of clinical records, periodically selecting a representative sample of clinical records of hypertensive patients and using a structured questionnaire – see annex 5 - to evaluate if the clinical records fulfil the requirements of a complete cardiovascular risk assessment interview and physical examination, doctors' adherence to the hypertension management guideline and some parameters to assess the quality of the provided health care. The CVRT will also provide regular active feedback and support to health professionals involved in the CVRP. It will also supervise the Healthy Hearts service.

A.3.2. Guideline-based standardized diagnostic and treatment protocols: before the start of the intervention, the diagnostic algorithm will be standardized and a simplified and implementable drug treatment algorithm will be defined, based on the national clinical guidelines and in agreement with the general direction of Metrosalud, the direction of the health area and the clinical staff. A core set of antihypertensive medications will be identified and primary and secondary options will be defined for each of the major pharmacologic classes of antihypertensive drugs (diuretics, angiotensin-converting enzyme inhibitors/angiotensin II receptor blockers, calcium channel blockers and Beta-blockers).

A.4. Availability of antihypertensive medications: the availability of the defined core set of antihypertensive medications will be assured through the central store of Metrosalud. Any (un-)availability of antihypertensive medications will be communicated to clinicians at the beginning of each week and *ad hoc* in case of intervening stock-out, in order to timely inform them on possible alternative prescription.

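### Indicator 36 sets every notification in a month against a count of weeks, so ad hoc stock-out notices, if logged, can mask missed weekly ones

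*Combined protocol and SAP*

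**What the plan says.** Section 4.2.1, A.4 (availability of antihypertensive medications) describes how clinicians are kept informed. Availability or unavailability "will be communicated to clinicians at the beginning of each week", and further notices go out ad hoc "in case of intervening stock-out, in order to timely inform them on possible alternative prescription". There are therefore two streams: a scheduled weekly notice, and an unscheduled notice triggered by a stock-out.

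Table 4, part D has two indicators for this component:

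- **Indicator 36**, "Notification on availability of core set of anti-hypertensive drugs". The numerator is "Total number of notifications made in a month", the denominator is "Number of weeks in the respective month", and the source is "Register of notification at the pharmacy service". It is collected monthly and broken down by type of health facility. No target, cap or split by kind of notice is given.
- **Indicator 37**, "Number of weeks without availability of one or more essential antihypertensive drugs". It has no denominator and comes from the pharmacy inventory, by type of facility and by drug.

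**The concern.** The numerator and denominator of indicator 36 do not describe the same thing. One start-of-week notice is due per week, so a denominator of weeks is right for the scheduled stream. The numerator is not limited to that stream. If ad hoc notices are also recorded, the ratio is not a proportion: it has no upper limit of 1, and a value of 1 does not mean that every weekly notice was sent.

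The error has a direction. Ad hoc notices arise from stock-outs, so the score is raised most in the months and facilities with the most stock-outs between weekly notices. The planned breakdown by type of facility would carry the same distortion.

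What is at stake is a frequency measure for the process evaluation, which is a secondary objective in section 2. Section 4.2.3 counts frequency among the parts of adherence, and section 4.3.2 asks whether components were delivered as often as planned. Indicator 36 is the only row of Table 4 that addresses this for the availability notices. Indicator 37 shows whether drugs were missing, not whether clinicians were told.

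**Working it through.** The plan gives no value or target for indicator 36, so there is no stated figure to reproduce. The check is direct arithmetic on the definition.

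**Inputs**

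- *W*, weeks in the month: the denominator in Table 4. Values of 4 and 5 are assumed here.
- *s*, scheduled weekly notices actually sent, from 0 to *W*: A.4 plans one per week. The number sent is assumed.
- *a*, ad hoc stock-out notices in the month: planned in A.4 with no number given. A range of 0 to 4 is assumed.
- Ad hoc notices are taken to be entered in the register and counted. The unrestricted total in the numerator reads this way, but the documents do not say so outright.

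**Formulas**

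- Indicator as written: (*s* + *a*) / *W*
- Weekly completion: *s* / *W*
- Excess of the first over the second: *a* / *W*, which is 1/4 = 0.25 per ad hoc notice in a 4-week month and 1/5 = 0.20 in a 5-week month
- The indicator reaches 1 or more whenever *a* ≥ *W* − *s*, so one ad hoc notice is enough to cover one missed week.

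**Results**

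| W | s | a = 0 | a = 1 | a = 2 | a = 3 | a = 4 | Weekly completion |
|---|---|---|---|---|---|---|---|
| 4 | 4 | 1.00 | 1.25 | 1.50 | 1.75 | 2.00 | 1.00 |
| 4 | 3 | 0.75 | 1.00 | 1.25 | 1.50 | 1.75 | 0.75 |
| 4 | 2 | 0.50 | 0.75 | 1.00 | 1.25 | 1.50 | 0.50 |
| 5 | 5 | 1.00 | 1.20 | 1.40 | 1.60 | 1.80 | 1.00 |
| 5 | 3 | 0.60 | 0.80 | 1.00 | 1.20 | 1.40 | 0.60 |

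Three quite different months all score 1.00:

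- all 4 weekly notices and no ad hoc notice: (4 + 0)/4
- 3 weekly and 1 ad hoc: (3 + 1)/4
- 2 weekly and 2 ad hoc: (2 + 2)/4

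Their weekly completion is 1.00, 0.75 and 0.50. With no ad hoc notices (the *a* = 0 column), the indicator equals weekly completion and works as intended.

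**Comparison with neighbouring rows.** Indicators 13, 25, 26, 27 and 32 each set what was done against what was programmed. Indicator 36 departs from that pattern only because unprogrammed events can enter its numerator.

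**The case against.** The strongest reply is that a denominator of weeks shows what the authors meant: the weekly notice. On that reading the ratio is simply weekly completion. Nothing states that ad hoc notices go into the register, and the annex list in section 12 includes no pharmacy notification register whose fields could be checked. This stands in part. The point concerns an ambiguity, not a demonstrated miscount. But the numerator asks for a total without restriction, and if only weekly notices were meant, the table should say so.

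The counts above are hypothetical. That stands, and they are labelled as assumptions. A value above 1 would also give itself away as containing extra notices. The misleading case is the one at or below 1, where ad hoc notices replace missed weekly ones.

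Two stronger readings are tempting, and the documents support neither:

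- *Poor drug supply could pass as full compliance.* Indicator 36 measures communication, not supply. A month with stock-outs in which every weekly notice was sent is rightly a month of full weekly notification. Supply is reported in the next row by indicator 37, from a different source.
- *The indicator could by itself cause the component to be classed as delivered.* It has no threshold. Under section 4.3.2, three evaluators judge independently from documents, interviews and observation notes, and all must agree before an aspect is classed as implemented. Section 4.2.3 adds monthly self-registration forms, checked by observation. Indicator 36 can inform that judgement but does not decide it.

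**Conclusion.** The point holds as a minor defect in one process indicator. As worded, indicator 36 mixes scheduled and unscheduled notices over a denominator that fits only the scheduled ones. It can therefore exceed 1, and it can reach 1.00 when weekly completion is 0.75 or 0.50 (4-week month, with 1 or 2 ad hoc notices).

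This rests on one inference, that ad hoc notices are entered in the register and counted. The size in practice depends on how many ad hoc notices and missed weeks occur, which the documents do not say. If no ad hoc notice is counted, there is no error.

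The consequence is limited to how the frequency of availability notices is reported in the process evaluation. What can be hidden is a missed weekly notice, not a shortage of drugs. The Table 1 gaps, the difference-in-difference analysis and the sample size are untouched.

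**What to change.** In Table 4, part D, change the numerator of indicator 36 to *number of weeks in the month with a start-of-week availability notification*, and keep the denominator. The result is a proportion between 0 and 1 that equals weekly completion.

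Report the number of ad hoc notices as a separate count, read alongside indicator 37. A ratio of ad hoc notices to stock-out events would be more informative, but it should not be promised yet: indicator 37 counts weeks, and nothing shows that the inventory records individual events.

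The cost is a small wording change in the table. The one practical requirement is that the register records the date or type of each notice, so a field must be added if it does not do so already.

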#### 4.3.2 Qualitative Data Analysis

Based on the logical model and the detailed description of the intervention, one to three process evaluation questions will be elaborated to determine whether each aspect of the intervention was implemented as intended (e.g. was each of the intervention components implemented as planned? Were the intervention components implemented as often and for as long as planned? Was the methodology and way of delivery followed as described?).

Semi-structured interviews with health providers involved in the implementation and project leaders or coordinators, as well as patients, will be conducted by a social scientist (outline of interview guides in annex 8 and 9). To determine if each intervention component was implemented as specified, the content of collected documents, semi-structured interviews, and observation notes from the same level, unit and actor will be analysed independently by three independent researchers (evaluators). The components will be categorized according to the analytical framework mentioned above (content, frequency, duration, and coverage) and also by establishing at which level (individual, team, organizational) adaptations are introduced. The analysis will be conducted systematically for every previously identified critical point.

Three types of adaptations to the original design of the intervention will be identified by the evaluators, following the categorization proposed by Rebchook et al.(22): deletion (when a component is omitted or modified so radically that the programme is no longer implemented as intended), modification (a component is implemented with minor or major modifications while still respecting the original purpose) and third, additional activities or components are added. The algorithm to categorize adaptation will be as follow: if all three evaluators independently agree that a given aspect of the intervention was implemented as specified, it will be classified as “implemented”. If all agree that a given component was not implemented, it will be classified as such. If any of the evaluators consider that a component was modified, it will be classified as such. Added components will be also identified. Modified and added aspects will be classified as positive or negative in relation to the expected outcome, taking into consideration the functioning principles. Those adaptions classified as negative will be corrected.

Besides, an inductive thematic analysis of the semi-structured interviews will be conducted to identify, define and organize participant responses regarding reasons for introducing adaptations and general factors either positively or negatively affecting or moderating implementation. Then, transcripts will be reviewed, using a constant comparative technique to expand or merge themes. Finally, findings will interpreted according to the six moderating factors pre-established by the

theoretical framework. Factors not matching the deductive coding scheme will be classified as intervention-specific moderating factors.

In depth interviews with patients will be analysed firstly inductively looking for experiences and views of the intervention across different stages and component of the intervention, as well as region and health centres within the commune. In a second stage, data will be reclassified according to the subcategories of fidelity and the moderating factors of the framework to triangulate with data provided by the implementers and with quantitative results.

The qualitative data analysis will be conducted by the social scientist. To increase internal validity, the senior sociologist not involved in data collection will review the data and consistency of the coding system. Besides, findings from the data analysis and triangulation with quantitative results will be discussed systematically with a wider group of the research team, composed of professionals with diverse backgrounds (epidemiologists, public health practitioners, health care managers, nurses and general practitioners).

To identify when and under which circumstances the intervention was successful we will used qualitative comparative analysis (QCA) by contrasting outcomes data with implementation data collected at different stages and critical points of the intervention along process evaluation. Qualitative analysis will be carried out using the software Nvivo v.10.

## 5. ETHICAL ISSUES

Confidentiality of the retrieved individual information will be guaranteed. The collected information will be used only for research purposes and at no time the identity of participating individuals will be disclosed.

During the endline survey, confidentiality at the time of interview will be also guaranteed interviewing participants belonging to the same household one by one and in separate spaces. All surveyors will be trained in identifying patients with severe abnormal conditions. They will identify and refer to the nearest health center, individuals with very high BP figures or reporting health complications or acute symptoms. In Colombia, health care for hypertension is free of charge in both regimes of the health insurance system (Subsidized and Contributory). Patients found to be hypertensive without follow-up or treatment will be referred for care to the provider of the corresponding patients' health insurance scheme.

Exit-interviews to patients will be anonymous and the identity of the consulting medical doctor or nurse won't be recorded. The results will be evaluated by the CVRT who will give collective

constructive feedback to the medical staff; the patient survey results won't be used as an individual evaluation of the medical staff.

The intervention does not pose any risk to beneficiaries and it implies the implementation into the routine setting of evidence based best practices. Any procedure that influences directly patient care has been agreed with the Metrosalud central authorities and site health staff. All activities are implemented under standard practice and, conditional on adjustment when needed, will continue beyond the end of the study period.

Patients eligible for the qualitative component, will be asked by the local health staff if they would be interested in learning more and participate in the study. If they are interested, they will be invited to participate by the PI or the research assistant at the health setting. Health staff will be contacted directly by the research staff. The objectives and procedures will be explained as well as the benefits and risks and written informed consent will be obtained (see below).

The research team will guarantee to allocate the most convenient place and time for interviews. A place as enclosed for privacy and as neutral as possible for participants will be chosen. Participants will be asked if they consent for the discussion to be tape-recorded.

## 5.1 Ethical (and regulatory) Review

This study protocol will be submitted for formal review and approval to the Institutional Review Board of ITM, the Ethics Committee of University of Antwerp Hospital and the Research Ethics Committee of Metrosalud E.S.E. No participants will be enrolled or participant related activities performed before written approval from these bodies is obtained.

The study will be carried out according to the principles stated in the Declaration of Helsinki, all applicable regulations and according to established national and international scientific standards.

## 5.2 Obtaining Informed Consents

Informed consent for participation in the study will be sought for the endline survey (Annex 10) and the qualitative component (Annexes 11 and 12). For the endline survey, during the household visit all eligible individuals will be explained about the study in lay language by the research team and handed over the informed consent form.

Participant information sheets will describe the purpose of the study, the procedures to be followed, the risks and benefits of participation, etc. Study participants will be informed that participation on

the study is completely voluntary and that they can withdraw from the study at any time without any negative consequences. A copy of the informed consent will be handed over to participants. No informed consent will be sought for other intervention components, as all implemented activities are part of routine practice.

### 5.3 Insurance

The Coordinator of this study, the Antwerp Institute of Tropical Medicine, has obtained an umbrella insurance for low risk research to cover any potential damage or loss to study participants and which is caused directly or indirectly by their participation in the study.

## 6. MONITORING AND QUALITY CONTROL

All research staff will be trained in responsible conduct of research. For the endline survey, the surveyors will be trained on the study, the study tools and BP measuring. For the intervention at health services, the participant health staff will be trained on the study procedures tools for data collection and self-reporting. They also will be subject of random supervision visits and audits to check the implementation of the planned activities, its accuracy and reliability. The PI will be responsible of the monitoring and quality control of the implementation of study procedures, data collection, entry and analysis. The qualitative component will be carried out by trained research staff.

## 7. TIMELINE

	Year 1				Year 2				Year 3			
	Q1	Q2	Q3	Q4	Q1	Q2	Q3	Q4	Q1	Q2	Q3	Q4
Preparation of the Intervention	■											
Ethical Approval of intervention protocol	■											
Intervention		■■■■■	■■■■■	■■■■■	■■■■■	■■■■■	■■■■■	■■■■■	■■■■■	■■■■■	■■■■■	■■■■■
Data collection		■■■■■	■■■■■	■■■■■	■■■■■	■■■■■	■■■■■	■■■■■				
Endline survey									■			
Data analysis				■■■■■	■■■■■	■■■■■	■■■■■	■■■■■	■■■■■	■■■■■	■■■■■	■■■■■
Dissemination of results						■■■■■	■■■■■	■■■■■	■■■■■	■■■■■	■■■■■	■■■■■

= intervention activities continue to be implemented by Metrosalud as part of routine practice

## 8. DATA MANAGEMENT AND ARCHIVING

### 8.1 Data Management

Data will be collected as described in section 4. Databases will be electronically encrypted, and a single study code will be assigned to each participant and they will be password-protected, with a password known only to the research team. The list of participant names and their assigned study codes will be stored in a separate database with restricted access to the study investigators that did the process of identification. Data will be analysed as described in section 4. The obtained individual information will be known only by the research team, where information access levels will be established, in particular for personal identification data. For the endline survey, questionnaires will be filled in by using tablets, and the information will be consolidated through an electronic platform provided by a professional statistics enterprise. The access to each electronic questionnaire is restricted to specifically authorized surveyor. The software of the electronic platform will allow to record in real-time every applied single questionnaire, obtaining reliable databases. Only aggregate data will be extracted from the billing and electronic clinical records of Metrosalud and from the databases of the subsidized regimen and of the non-insured poor population. Qualitative information will be transcribed *verbatim* by trained personnel. Transcripts and data will be stored in Nvivo v.10 and analysed as described in section 4.3.2. Anonymity of participants will be maintained, a code will be assigned to every participant and transcripts will be anonymous for transcribers. Data protection and confidentiality will be responsibility of the PI and the responsible for qualitative analysis.

